4.5. Safety Population

The safety population will include all subjects who receive at least 1 dose of study treatment, with subjects grouped according to their actual treatment. If GB001 was taken, subjects will be grouped according to the highest dose of GB001 actually taken (20 mg, 40 mg, or 60 mg) based on kit and study treatment accountability data. The safety population will be utilized for safety and PK analyses.

5. STUDY PATIENTS

5.1. Disposition of Patients

The disposition of subjects will be summarized for the all enrolled population. The number and percent of subjects who are screened, screen failures, run-in participants, completed run-in, and run-in failures, along with screen failure reasons, run-in failure reasons, and reasons not randomized will be summarized overall. In addition, the number and percent of subjects who are randomized, treated, completed study treatment, discontinued study treatment, completed the study, and withdrew from the study, along with associated reasons, and in each analysis population, will be summarized by treatment group and overall.

Disposition data will also be presented in a by-subject data listing. In addition, a listing of the randomization scheme will be presented.

5.2. **Protocol Deviations**

Protocol deviations will be identified and reviewed on an ongoing basis by the study team and entered into a Clinical Trial Management System. Significant protocol deviations are defined as those that can affect efficacy and/or safety assessments, the safety or mental integrity of a subject, or the scientific value of the study. Protocol deviations will be classified as significant or non-significant and will be assigned a protocol deviation type prior to unblinding. The number and percent of subjects with at least 1 significant protocol deviation overall and for each protocol deviation type will be summarized for the ITT population.

Protocol deviations will also be presented in a by-subject data listing. In addition, subjects who were randomized in error and subjects who were mis-stratified for ICS dose (medium or high) at randomization may be presented in a by-subject data listing.

6. DEMOGRAPHIC AND OTHER BASELINE CHARACTERISTICS

6.1. Demographic Characteristics

Demographic characteristics will be summarized for the ITT and per protocol populations for the following parameters:

- Age (years; cts; $\geq 18 < 50$, $\geq 50 < 65$, ≥ 65)
- Sex (male, female)
- Race (White, Black or African American, American Indian or Alaska Native, Native Hawaiian or Other Pacific Islander, Asian, Other)
- Ethnicity (Hispanic or Latino, Not Hispanic or Latino, Not Reported)
- Height (cm; cts)
- Weight (kg; cts)
- Body mass index (BMI [kg/m²; cts; < 18.5, \geq 18.5, \geq 25-< 30, \geq 30])
- Country (Austria, Belgium, Canada, Czech Republic, France, Germany, Poland, Spain, Ukraine, United Kingdom, United States)
- Region (North America [United States, Canada], Eastern Europe [Czech Republic, Poland, Ukraine], Western Europe [Austria, Belgium, France, Germany, Spain, United Kingdom])

Demographic characteristics will also be presented in a by-subject data listing.

6.2. Baseline Disease Characteristics

Baseline disease characteristics will be summarized for the ITT and per protocol populations for the following parameters:

- ICS dose at Randomization and actual (medium, high)
- Asthma duration (years; cts)
- Triggers of exacerbations (air pollution, allergy, aspirin, etc.)
- Total number of exacerbations in the past 12 months (cts; 0, 1, 2, 3, ≥ 4; overall and by exacerbation categories [treated with systemic corticosteroids, resulted in an emergency department visit, resulted in a hospitalization])
- Uncontrolled asthma demonstrated by the following:
 - 2 or more asthma exacerbations requiring treatment with systemic corticosteroids in the 12 months prior to Screening Visit
 - Previously confirmed history of 1 asthma exacerbation requiring treatment with systemic corticosteroids in the 12 months prior to Screening Visit and ACQ-5 score of \geq 1.5 at Screening Visit

- Chronic Rhinosinusitis and Nasal Polyps (neither, chronic rhinosinusitis and nasal polys, chronic rhinosinusitis without nasal polys, nasal polys without chronic rhinosinusitis)
- Smoking history (former smoker [yes, no]; cigarette pack-years)
- Alcohol history (never, former, current)

Baseline disease characteristics will also be presented in by-subject data listings.

6.3. Atopic/Allergic Conditions

Atopic/allergic conditions will be summarized for the ITT and per protocol populations for the following parameters:

• Allergic Rhinitis, Anaphylactic Reaction, Aspirin-exacerbated Respiratory Disease, Atopic Dermatitis, Chronic Rhinosinusitis, Food Allergy, Nasal Polyps, Urticaria (none, ongoing, past)

Atopic/allergic conditions will also be presented in a by-subject data listing.

6.4. Efficacy-Related Baseline Characteristics

Efficacy-related baseline characteristics will be summarized for the ITT and per protocol populations for the following parameters:

- Pre-bronchodilator FEV₁ at Screening and Baseline (L; cts)
- Post-bronchodilator FEV₁ at Screening (L; cts)
- Pre-bronchodilator percent predicted FEV₁ at Screening (%; cts; $< 60, \ge 60$)
- Post-bronchodilator percent predicted FEV₁ at Screening (%; cts)
- Pre-bronchodilator FEV₁/forced vital capacity (FVC) at Screening and Baseline (ratio; cts; < 0.7, ≥ 0.7)
- FEV₁ reversibility at Screening (%; cts)
- AM PEF over last 7 days of the Run-in (L/min; cts)
- Rescue medication usage over last 7 days of the Run-in (puffs/day; cts)
- ACQ-5 score at Baseline (cts; $< 1.5, \ge 1.5$)

Efficacy-related baseline characteristics will also be presented in a by-subject data listing.

6.5. Biomarker Baseline Characteristics

Biomarker baseline characteristics will be summarized for the ITT and per protocol populations for the following parameters:

- Qualifying blood eosinophils (GI/L; cts; ≥ 0.25 , ≥ 0.30 , ≥ 1.50)
- Blood eosinophils at Baseline (GI/L; cts; < 0.20, \geq 0.20; < 0.25, \geq 0.25; < 0.30, \geq 0.30; < 1.50, \geq 1.50)
- Qualifying and Baseline blood eosinophils (GI/L; ≥ 0.25 and < 0.25; ≥ 0.30 and < 0.30)
- Fractional exhaled nitric oxide (FeNO) at Screening (ppb; cts; $< 25, \ge 25; < 30, \ge 30;$ $< 35, \ge 35; < 50, \ge 50$)
- FeNO at Baseline (ppb; cts; < 25, ≥ 25; < 30, ≥ 30; < 35, ≥ 35; < 50, ≥ 50)
- Screening and Baseline FeNO (ppb; ≥ 25 and < 25; ≥ 30 and < 30; ≥ 35 and < 35; ≥ 50 and < 50)
- Baseline blood eosinophils and Baseline FeNO categories (all combinations for 0.25 and 25; 0.25 and 30; 0.25 and 35; 0.25 and 50; repeat for 0.30)
- Immunoglobulin E (IgE) at Baseline (IU/mL; cts; normal [\leq 158], high [> 158])
- 25-Hydroxyvitamin D at Baseline (ng/mL; cts; $\leq 20, > 20$)
- Chloride at Baseline (mmol/L; cts; ≤ Quartile 1, > Quartile 1-≤ Quartile 2, > Quartile 2-≤ Quartile 3, > Quartile 3, where quartiles are based on the ITT population)

Biomarker baseline characteristics will also be presented in a by-subject data listing.

6.6. **Prior Medications**

Verbatim prior medication terms will be coded to a drug class (anatomical therapeutic chemical [ATC2]) and PT using World Health Organization (WHO)Drug Global B3 March 2018 or later. Prior medications are defined as all medications that started prior to the date of first dose of study treatment. In general, if it is not clear whether a medication is prior due to missing or incomplete medication start date, the medication will be considered to be prior unless the non-missing portions of the start date indicate otherwise. Counting will be by subject and at each level of summarization (e.g., any medication, ATC2, and PT), subjects receiving more than one medication will be counted only once.

Prior medications will be summarized for the safety population.

6.6.1. Prior Asthma Medications

Prior asthma controller medications will be summarized for the ITT population.

Prior asthma biologic medications will be summarized and include, but are not limited to, those with a PT in the following list: mepolizumab, benralizumab, omalizumab, and dupilumab.

In addition, prior leukotriene receptor antagonist (LTRA) (e.g., montelukast) use will be summarized.

Lastly, the number and percent of subjects who received an ICS plus a long-acting beta-agonist (LABA), who received an ICS plus a LABA plus a long-acting muscarinic antagonist (LAMA), and who received an ICS plus a LABA plus a LTRA will be summarized.

6.7. Concomitant Medications

Verbatim concomitant medication terms will be coded to a drug class (ATC2) and PT using WHODrug Global B3 March 2018 or later.

Concomitant medications are defined as all medications that started on or after the date of first dose of study treatment or that started prior to the date of first dose of study treatment and stopped on or after the date of first dose of study treatment or were ongoing. In general, if it is not clear whether a medication is concomitant due to missing or incomplete medication start and/or end dates, the medication will be considered to be concomitant unless the non-missing portions of the start and end dates indicate otherwise.

A medication may be considered as both prior and concomitant i.e. prior and concomitant medications are not mutually exclusive. Counting will be by subject and at each level of summarization (e.g., any medication, ATC2, and PT), subjects receiving more than one medication will be counted only once.

Concomitant medications will be summarized for the safety population. Prior and concomitant medications will also be presented in a by-subject data listing and will include an indicator, identifying each medication as prior and/or concomitant.

6.7.1. Concomitant Asthma Medications

Concomitant asthma controller medications will be summarized for the ITT population. In addition, concomitant LTRA (e.g., montelukast) will be summarized for the ITT population.

Lastly, the number and percent of subjects who received an ICS plus a LABA, who received an ICS plus a LABA plus a LAMA, and who received an ICS plus a LABA plus a LTRA will be summarized for the ITT population.

7. EXTENT OF EXPOSURE, COMPLIANCE, AND TIME ON STUDY

7.1. Extent of Exposure

Duration of study treatment (days, weeks, and subject-years) will be summarized for the safety population using descriptive statistics and categorically (every 4 weeks). Duration of study treatment will also be presented in a by-subject data listing.

7.2. Compliance

Compliance with study treatment will be assessed using the following formula:

Treatment compliance (%) = (# of actual tablets taken/# of expected tablets) x 100,

where # of actual tablets taken = (# of tablets dispensed - # of tablets returned) and # of expected tablets is based on actual duration of study treatment

Compliance will be summarized for the safety population using descriptive statistics and categorically ($< 80, \ge 80-100, > 100-< 120, \ge 120$).

Compliance with study treatment will also be presented in a by-subject data listing. In addition, IP accountability including kit information will be presented in a by-subject data listing.

7.3. Time on Study

Time on study (days, weeks, and subject-years) will be summarized for the safety population using descriptive statistics and categorically (every 4 weeks). The latest assessment date for each subject will be used in the calculation of time on study. Time on study will also be presented in a by-subject data listing.

8. EFFICACY EVALUATION

8.1. Overview of Efficacy Analysis Issues

8.1.1. Handling of Dropouts or Missing Data

A variety of methodological approaches will be applied for handling subjects with missing data; full details are provided in Section 8.3.

8.1.2. Multicenter Studies

Data from all countries and sites will be pooled for the purpose of analyses.

8.1.3. Multiple Comparisons/Multiplicity

In general, statistical testing of efficacy endpoints will be made without any adjustments for multiplicity, and all statistical hypothesis tests will be two-sided with a significance level of 0.050.

8.2. Efficacy Endpoints

Table 1 provides a summary of the statistical models/methods of primary and sensitivity analyses to be used for the primary, secondary, and select tertiary/exploratory endpoints. For all efficacy analyses, ICS dose stratification factor values used for randomization will be used as a covariate and results will be summarized for the ITT population, unless otherwise stated.

Efficacy Endpoints	Missing Data	Logistic Regression		ANCOVA		MMRM		Cox	Negative
Lindpoints	Threshold ^a	without	with	Alv with	without	with	without	Propor- tional	Binomial Regres-
		MI	MI	MI	MI	MI	MI	Hazards	sion ^b
Primary									
Proportion of subjects who experience worsening of asthma by Week 24		P, S	S						
Secondary									
Change from baseline to Week 24 in	< 5%				Р		S		
ACQ-5 score	$\geq 5\%$			Р	S	S	S		
Change from baseline to Week 24 in pre-	< 5%				Р		S		
bronchodilator FEV_1	$\geq 5\%$			Р	S	S	S		
Time to first asthma worsening								Р	
Annualized rate of severe asthma exacerbations									P, S
Change from baseline to Week 24 in post-	< 5%				Р				
bronchodilator FEV_1	$\geq 5\%$			Р	S				
Change from baseline	< 5%				Р		S		
to Week 24 in AM PEF	≥ 5%			Р	S	S	S		
Tertiary/Exploratory									
PROs									
Proportion of subjects with a greater than or equal to 0.5 decrease in ACQ-5 score at any time post-baseline		Р							
Change from baseline to Week 24 in AQLQ-S					Р				
Change from baseline to Week 24 in SNOT-22					Р				
Change from baseline to Week 24 in hair- loss assessment ^e									
Additional Markers									
of Asthma Control				ļ					
Change from baseline to Week 24 in rescue medication use					Р				

 Table 1:
 Efficacy Endpoints and Analysis Methods

Efficacy Endpoints	Missing Data	Logistic Regression		ANCOVA		MMRM		Cox Propor-	Negative Binomial
Ihre	Threshold ^a	without MI	with MI	with MI	without MI	with MI	without MI	tional Regres- Hazards sion ^b	
Change from baseline to Week 24 in daily asthma symptom scores					Р				
Change from baseline to Week 24 in awakening at night due to asthma symptoms requiring rescue medication use					Р				
Biomarkers									
Change from baseline to Week 24 in FeNO					Р				
Percentage change from baseline to Week 24 in FeNO					Р				
Change from baseline to Week 24 in sputum eosinophils and neutrophils		DM	1		P				

ANCOVA = analysis of covariance; MMRM = mixed-effects model with repeated measures; MI = multiple imputation; P = primary; S = sensitivity

^a The analysis approach depends on the amount of missing data for the endpoint in the ITT population.

^b If the distribution of severe exacerbation data is underdispersed, or if the negative binomial regression model fails to converge, a Poisson regression model will be used instead.

^c Cross tabulations of the Baseline assessment versus the Week 24 assessment for Norwood classification (males) and Savin classification (females) separately.

8.3. Analysis Methods

8.3.1. Primary Efficacy Analyses

The primary endpoint is the proportion of subjects who experience worsening of asthma by Week 24 as defined by at least one of the following:

- On 2 consecutive days, AM PEF \leq 75% of mean AM PEF measured over the last 7 days of the Run-in
- $FEV_1 < 80\%$ of baseline (Visit 2)
- Increase in rescue medication use of ≥ 6 puffs/day on 2 consecutive days compared to mean use over the last 7 days of the Run-in
- Increase in ACQ-5 score of ≥ 0.5 compared to baseline (Visit 2)
- The occurrence of a severe asthma exacerbation (asthma attack) defined as deterioration of asthma that leads to the use of systemic corticosteroids for at least 3 days, hospitalization, or an Emergency Department visit

Logistic regression modeling will be used to compare each GB001 group with placebo. The model will include covariates for treatment group, ICS dose (medium or high) at randomization, region (North America, Eastern Europe, Western Europe), baseline pre-bronchodilator FEV₁, and baseline ACQ-5 score. If the full model does not converge, a model with treatment group, ICS dose at randomization, and region as covariates will be utilized. If this reduced model does not converge, a model with treatment group and ICS dose at randomization will be used. In the rare case that convergence issues remain, only treatment group will be included in the model.

The number and proportion of subjects meeting the primary endpoint and corresponding 95% Wilson (Score) CIs (Wilson, 1927) will be summarized by treatment group. ORs, corresponding asymptotic 95% CIs along with the absolute differences and corresponding 95% CIs, and p-values will be summarized for each GB001 group versus placebo. The 95% CIs for the absolute difference will be Newcombe continuity-corrected CIs (Newcombe, 1998). Percentage reductions and corresponding 95% CIs will also be summarized. Lastly, the number and proportion of subjects meeting each component of the primary endpoint, with observed worsening of asthma, and with an assigned status of asthma worsening will also be summarized by treatment group. Subjects can meet more than one component of the primary endpoint.

A subject who prematurely withdraws from the study without experiencing asthma worsening will be assigned asthma worsening status by Week 24 (yes/no) based on their discontinuation of study treatment and withdrawal from study reasons as summarized below in Table 2. If a subject's reason for discontinuation of study treatment or withdrawal from study is indicative of lack of efficacy or is an AE indicative of asthma worsening, a determination will be made prior to study unblinding for the interim analysis regarding whether the subject should be considered to have had asthma worsening for the primary endpoint. Otherwise, subjects who prematurely withdraw from the study will be considered to have not experienced asthma worsening for the primary endpoint.

Table 2:Criteria for determination of asthma worsening status for subjects who
prematurely withdraw from the study without experiencing asthma
worsening

Reason for Discontinuation of Study Treatment and/or Withdrawal from Study	Asthma Worsening Status Assigned (Yes/No)
Lack of Efficacy	Yes
AE where the corresponding AE PT reflects asthma worsening including 'asthma'	Yes
Death where death is due to an SAE where the corresponding SAE PT reflects asthma worsening including 'asthma'	Yes
Lost to follow-up, Non-compliance with study drug, Physician decision, Protocol deviation, Withdrawal by Subject, or Other, where further details indicate asthma, asthma worsening, lack of efficacy or prescription of or switch to a new asthma treatment	Yes
AE where the corresponding AE PT does not reflect asthma worsening	No
Death where death is due to an SAE where the corresponding PT does not reflect asthma worsening	No
Lost to follow-up, Non-compliance with study drug, Physician decision, Protocol deviation, Withdrawal by Subject, or Other, where further details do not indicate asthma, asthma worsening, lack of efficacy or prescription of or switch to a new asthma treatment	No

A bar graph of the proportion of subjects meeting the primary endpoint by treatment group and a bar graph of the proportion of subjects meeting each component of the primary endpoint by treatment group will be provided.

The primary endpoint and components will also be presented in a by-subject data listing.

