4.2. Scientific Rationale for Study Design

4.2.1. Study Population

The target population is patients with moderate to severe asthma who are currently receiving GINA step 4 or 5 therapy and have evidence of eosinophilic inflammation. Reducing eosinophilic inflammation within the lungs, assessed by measuring sputum eosinophils, has been associated with a reduction in asthma exacerbations (Haldar, 2009; Pavord, 2012). It is anticipated that GB001, as a DP₂ antagonist, will reduce sputum eosinophilia and consequently asthma exacerbations. As measurement of sputum eosinophils is cumbersome and requires sites experienced with this procedure to obtain appropriate samples, a surrogate measure of lung eosinophils, namely peripheral blood eosinophils, will be used in this study. The cut-off threshold of 250 cells/μL has been selected for this study as it is predicted to have a sensitivity of 84% and a specificity of 91% to differentiate less than versus $\geq 3\%$ sputum eosinophils (Wagener, 2015).

Based upon regulatory guidance, patients with a history of asthma exacerbations should be recruited in studies where the primary endpoint is exacerbation reduction (EMA, 2015). Patients with a history of exacerbations are more likely to experience future exacerbations. Therefore, this study will be recruiting subjects with a history of at least 1 asthma exacerbation in the previous 12 months.

In addition, DP₂ antagonists might have an effect in a subset of subjects with inflammation beyond the lower airways such as upper airways and skin. Thus, exploratory assessments targeting these tissues will evaluate additional beneficial effects as a result of treatment with GB001.

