2.5. Sample Size Determination

A total sample size of approximately 480 subjects (approximately 120 per treatment group, randomized in a 1:1:1:1 ratio) is estimated to provide 80% power to detect a reduction in odds of 66% between each GB001 group and placebo at an 0.050 two-sided level of significance for the primary endpoint of the proportion of subjects who experience worsening of asthma by Week 24. This assumes the proportion of subjects who experience worsening of asthma by Week 24 is 25% in the placebo group and 10.2% in each GB001 group and a dropout rate of 8%.

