8.3.2.3. Annualized Rate of Severe Asthma Exacerbations

A severe asthma exacerbation is defined as deterioration of asthma that leads to the use of systemic corticosteroids for at least 3 days, hospitalization, or an Emergency Department visit. Exacerbations for which the courses of systemic corticosteroids are separated by 7 or more days will be counted as separate severe asthma exacerbations.

The number and proportion of subjects with 0, 1, and ≥ 2 severe exacerbations and the annualized rate of severe asthma exacerbations will be summarized. The unadjusted annualized rate of severe exacerbations will be calculated as the total number of severe exacerbations divided by the total number of subject-years of follow-up and will also be summarized.

The total number of severe exacerbations will be analyzed using a negative binomial regression model, with the logarithmic transformation of follow-up time as the offset parameter. The follow-up time is defined as the subject's time on study up to and including Day 174. The model will include terms for treatment group, ICS dose (medium or high) at randomization, region, age at screening, and the number of exacerbations in the past 12 months. If the distribution of severe exacerbation data is under dispersed, or if the negative binomial regression model fails to converge, a Poisson regression model will be used instead of the negative binomial regression model. Exacerbations for which the courses of systemic corticosteroids are separated by 7 or more days will be counted as separate exacerbations.

Rate ratios for each GB001 group versus placebo, corresponding 95% CIs, and p-values will be provided from the model. In addition, the rate ratios and corresponding 95% CIs for the 3 pairwise comparisons among each of the GB001 treatment groups will be provided (60 mg vs 20 mg, 60 mg vs 40 mg, 40 mg vs 20 mg). Lastly, percentage reductions and corresponding 95% CIs will also be provided.

A sensitivity analysis will be performed to include asthma exacerbations that were treated with an intramuscular (IM) injection of systemic corticosteroids for less than 3 days. In this analysis, a severe asthma exacerbation will be defined as deterioration of asthma that leads to the use of oral or intravenous systemic corticosteroids for at least 3 days, the use of IM systemic corticosteroids for at least 1 day, hospitalization, or an Emergency Department visit.

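### The primary logistic and Cox models are valid as written but forgo a small precision gain by leaving out the prior-year exacerbation count

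*SAP*

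**What the plan says.** SAP 8.3.1 sets a logistic model with treatment group, ICS dose at randomization, three-level region, "baseline pre-bronchodilator FEV₁, and baseline ACQ-5 score". Protocol 9.4.1.1 names the same factors. SAP 8.3.2.2 gives the Cox model the same adjustment. All sensitivity analyses in SAP 8.3.1.1 reuse the primary model, so none adds exacerbation history.

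The negative binomial model in SAP 8.3.2.3 has a different set: besides treatment and ICS dose it includes "region, age at screening, and the number of exacerbations in the past 12 months".

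The count is available. Exacerbation history is taken at Screening (protocol 1.3) and the prior-year total is tabulated at baseline with a top category of 4 or more (SAP 6.2). It is also a subgroup factor for the primary endpoint, split as 1 versus more than 1 (SAP 8.4). Randomization is stratified by ICS dose and country only (SAP 2.4).

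On prognosis, protocol 4.2.1 says: "Patients with a history of exacerbations are more likely to experience future exacerbations".

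**The concern.** Severe exacerbation is one of the five components of the primary composite. The sponsor already adjusts for prior-year count when that component is analysed alone, but not when it is part of the composite. Because the count is not a stratification factor, only the model can account for a chance imbalance in it. The existing covariates need not stand in for it: inclusion criterion 9 admits subjects with one prior exacerbation only if Screening ACQ-5 is at least 1.5, but subjects with two or more at any ACQ-5. That rule pushes count and ACQ-5 in opposite directions among those enrolled.

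At stake is a modest amount of precision on the main comparison, obtainable from a baseline value that is already planned for collection.

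**Working it through.** **Reproducing the plan's figure.** SAP 2.5 says the sample size "is estimated to provide 80% power to detect a reduction in odds of 66% between each GB001 group and placebo". Inputs from that section: risks 25% and 10.2%, two-sided alpha 0.050, 80% power, 8% dropout, about 120 per group.

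- Odds ratio = (0.102/0.898) / (0.25/0.75) = 0.341, a 66% reduction in odds.
- Wald test on the log odds ratio: n = (1.960 + 0.842)² × [1/(0.25 × 0.75) + 1/(0.102 × 0.898)] / (ln 0.341)² = 110.05 evaluable per group.
- 110.05 / 0.92 = 119.6, or about 120. Power at 110 evaluable is 0.800.

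The plan's figure is reproduced with no covariate, so omitting the count takes nothing from it. The pooled two-proportion formula gives 0.826 at 110, close to the simulated values below.

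**What adding the count could give.** The documents state no association between count and composite, so its strength is assumed and shown as a range. Marginal risks are held at 25% and 10.2%, with 110 evaluable per arm.

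*Count predicts the whole composite; base model with treatment only.* 6,000 simulated trials per row; assumed shares of subjects with 1/2/3/4 prior events as shown; power without → with the count:

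| OR per prior event | 50/30/12/8% | 35/35/18/12% |
|---|---|---|
| 1.0 | 0.828 → 0.828 | 0.820 → 0.822 |
| 1.3 | 0.822 → 0.827 | 0.825 → 0.829 |
| 1.5 | 0.824 → 0.839 | 0.825 → 0.836 |
| 2.0 | 0.827 → 0.856 | 0.830 → 0.855 |
| 2.5 | 0.834 → 0.886 | 0.822 → 0.871 |

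Monte Carlo error is about 0.5 point per power figure.

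*Count predicts the whole composite; base model with the SAP's covariates.* Four arms of 110, criterion 9 applied, assumed mix 40/35/15/10%, 4,000 trials per row. Only count and treatment drive the outcome:

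| OR per prior event | Without | With | Gain (points) |
|---|---|---|---|
| 1.0 | 83.2% | 83.1% | −0.1 |
| 1.3 | 83.5% | 83.9% | 0.4 |
| 1.5 | 83.4% | 84.1% | 0.7 |
| 1.8 | 82.9% | 84.4% | 1.5 |
| 2.2 | 83.4% | 86.1% | 2.7 |

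With the same mix and treatment as the only base term, power at OR 2.2 rises from about 82% to 86%, or 4 points. So the gain at OR 2.2 is about 3 to 4 points, depending on the base model. Under these assumptions the entry rule alone gave a count–ACQ-5 correlation of about −0.20 (count and ACQ-5 independent before the rule, ACQ-5 mean 2.0, SD 0.9, no change from Screening to baseline).

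*Count predicts only the severe-exacerbation component.* Same 40/35/15/10% mix, 4,000 trials per scenario. The component's share of the composite risk is assumed:

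| OR per event for the component | Gain, share one half | Gain, share one third |
|---|---|---|
| 1.5 | 0.2 points | 0.3 points |
| 1.8 | 0.7 points | 0.5 points |
| 2.2 | 1.6 points | 0.8 points |

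A separate run at a share of one half gave 0.2 to 1.3 points. The implied odds ratio for the composite, two versus one prior events on placebo, is only 1.12 to 1.33.

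**Effect on the estimate.** With the marginal odds ratio fixed at 0.341, the odds ratio conditional on the count is 0.337 at OR 1.3, about 0.31 at OR 2.0 and about 0.29 at OR 2.5.

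No calculation was made for the Cox model.

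**The case against.** The strongest reply is that this is an optional refinement. Protocol and SAP agree on the primary covariates. The test is valid without the count, which is not a stratification factor. Covariates may reasonably differ by endpoint: the negative binomial model drops FEV₁ and ACQ-5 and adds age and history. All of that stands.

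A reader might infer that the protocol itself calls the count predictive of the primary endpoint. It does not. The sentence in 4.2.1 concerns having a history and future exacerbations, and it supports requiring at least one. Every eligible subject meets that requirement, so the contrast does not vary within the trial. Four of the five components are PEF, FEV₁, rescue use and ACQ-5, each judged against the subject's own baseline. A strong effect on the whole composite is also demanding: OR 2.2 per event means 2.2³ = 10.6-fold odds for four versus one prior events.

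The subgroup analysis in SAP 8.4 already fits history to the primary endpoint, but as a two-level factor with an interaction. It does not supply the main estimate and does not cover the Cox model. The change also reaches further than one term, because several other models borrow the primary covariates.

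What survives is narrow: a prespecified baseline adjustment that costs essentially no power in these simulations if the count is uninformative, and helps a little if it is informative.

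**Conclusion.** The primary logistic and Cox models are sound and the logistic comparison has its planned power, but they leave a small gain unused. For the logistic model it is nil if the count is not prognostic, roughly 0 to 1.5 points if it acts mainly through severe exacerbations, and about 3 to 4 points only if it strongly predicts the whole composite (OR about 2.2 per event). These sizes rest on assumed count distributions, assumed odds ratios and, for the component case, an assumed share of risk. The gain beyond the existing covariates was examined only with those covariates unrelated to outcome. The Cox gain is unknown.

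A reader might go further and infer bias, a shortfall against the planned 80%, or a contradiction between models. The documents support none of these: randomization protects the comparison, the sample size rests on no covariates, and the two adjustment sets belong to different endpoints. The point is low in severity.

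**What to change.** Before the interim unblinding, by which SAP 1 says the plan is final:

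- Add the prior-year exacerbation count to the models in SAP 8.3.1 and 8.3.2.2. State its form, for example continuous and capped at 4 to match the top category in SAP 6.2.
- In the convergence fallback of SAP 8.3.1, drop it at the same step as baseline FEV₁ and ACQ-5.
- Record the departure from protocol 9.4.1.1, which names the primary model.
- State whether the term carries into models that refer to the primary covariates: the multiple imputation (8.3.1.1.4), the secondary ANCOVAs (8.3.2.1) and the exploratory models (8.3.3.1.1 to 8.3.3.1.3 and 8.3.3.2.1).

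If the primary model is regarded as locked, a prespecified sensitivity analysis with the count is the minimum.

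The cost is one extra parameter, a slight shift in the conditional odds ratio, and aligning the SAP sections listed. The sample size stays at about 480.
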